The calculation of sample size was based on the question: "Which of the applied caries treatment methods will have the least frequency of complication occurrences, treating severe early childhood caries in children from the ages of 2 to 6 years-old?" Since we will compare proportions in six groups, in the sample size calculation we used formulas, which are shown in Fig 1 (Shao, Chow and Wang, 2003), calculating that the planned number of various proportions for comparison will be 9.

From previous studies it is known that conventionally treating early childhood tooth caries, the frequency of complications is 10% (Innes *et al.*, 2013), but, examining clinical cards at RSU's Institute of Stomatology Children's Dentistry department, the frequency of complications for children that are waiting in line for treatment with general anaesthesia and who receive no additional treatment, is approximately 30%, therefore in the study's treatment groups we expect that the frequency of complications will be no greater than 10%, but in the placebo groups - 30%. From the calculations in the formulas above, we calculated, that for the study we need 49 children in each group, to ascertain the difference in complication proportions between 30% un 10% with α error 0.05 and with a study capacity of 80%. Together 294 children are necessary but, calculating possible losses during the observation time, it is planned to involve 70 children in each group, therefore, 420 in six groups.

$$n = (p_A(1 - p_A) + p_B(1 - p_B)) \left(\frac{z_{1-\alpha/(2\tau)} + z_{1-\beta}}{p_A - p_B} \right)^2$$

$$1 - \beta = \Phi(z - z_{1-\alpha/(2\tau)}) + \Phi(-z - z_{1-\alpha/(2\tau)}) \quad , \quad z = \frac{p_A - p_B}{\sqrt{\frac{p_A(1-p_A)}{n} + \frac{p_B(1-p_B)}{n}}}$$

Fig 1. Formulas to calculate the sample size. n = the sample size (for one comparison, therefore two equivalent groups); Φ = standard normal allocation function; α = I type error; τ = number of comparisons; β = II type error; $1-\beta$ = study capacity.

Randomization, allocation and blinding

Flow chart of research methodology is shown in Fig 2. If the patient fulfills the inclusion criteria, their parents (caregiver) will be offered the opportunity to participate in the study. The objective of the study will be explained both verbally and in writing, as well as the expected results and side effects of the treatments:

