- 4) the level and development of the caries damage and activity (ICDAS, Nyvad criteria).

Outcome measures:

- I. Primary outcome measures:
 - A. Pain history during the observation period, assessed as Yes/No at 12 months follow-up visit.
 - B. Abscess history during the observation period, assessed as Yes/No at 12 months follow-up visit.
 - C. The number of newly extracted or otherwise surgically treated teeth during the observation period, assessed as a number of extracted teeth during the last year at 12 months follow-up visit.
- II. Secondary outcome measures:
 - A. The change in the overall activity of caries as Active/Non-active, assessed at 12 months follow-up visit.
 - B. The progression and change of activity of every lesion, assessed by ICDAS (for progression) and Nyvad (for activity) criteria, at 12 months follow-up visit.
 - C. The parent’s satisfaction with the way their children’s teeth look, assessed by questionnaire, asking: “Are you satisfied with the way your child’s teeth look?”

- and “Would you agree to repeat the treatment procedure used?”, both measurements in 5-point Likert scale, assessed at 12 months follow-up visit.
- D. The child’s satisfaction with their teeth, measured by the visual analogue scale (VAS) with 3 points - happy, not sure, sad, assessed at 12 months follow-up visit.
 - E. The child’s feelings during the treatment, measured by the modified Wong-Baker scale with 3 options - no hurt, hurts a little, hurts a lot), assessed during every appointment (depending on treatment group can be assessed at baseline, 1, 2, 3 weeks and 12 months; or at baseline, 6 and 12 months).
 - F. The direct costs of the treatment and the cost-effectiveness, calculated as EUR spent per treatment protocol; EUR per prevented major complications (in patient-level - pain, abscess, extraction) and EUR per prevented minor complications (in tooth-level - progression of caries lesion), the calculation will be made at 12 months follow-up.
 - G. The treatment method’s undesirable side effects, assessed by parents’ questionnaire at the 12 months follow-up visit.

Statistical analysis

Data will be digitized, by entering in an ad-hoc form in the Google Docs programme. Further the data will be exported cvs (comma separated values) to an archive. Missing data will be eliminated from the analyses, marking them NA.

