4. **WP4** Clinical trial. **The objective of WP4** is to perform the clinical trial according to an established protocol and the highest ethical standards with the primary aim of finding out which high-concentration fluoride application method and which application protocol more effectively protects pre-school children from complications arising from early childhood dental caries. Secondary objectives are to evaluate at which stage of development (cariou lesions) the methods are the most effective; which fluoride application method and protocol is more effective in arresting non-cavitated and cavitated cariou lesions in preschool children; how satisfied are parents and patients with SDF and Tiefenfluorid application procedures and side-effects (staining) and what are the costs and cost-effectiveness of each method and application protocol.
 1. Enrolment of patients in the study. General staff will offer suitable patients the chance to register for the procedures. A calibrated examiner (postdoctoral researcher) will inform parents about all details of the study. If the offered is accepted, parents sign the informed consent form.

2. Initial examination and interviewing of enrolled patients and their parents by a calibrated examiner (postdoctoral researcher).
3. Random allocation in six intervention groups. This will be done by a calibrated examiner (postdoctoral researcher) using six closed envelopes containing colour codes.
4. Performing interventions according to the protocol of each study group. Those interventions will be done by Intervention Staff (IS) - four trained postgraduate students and assistants (dental hygiene students).
5. Performing and documenting emergency treatment during the follow-up period. Done by trained general staff on a daily basis according to patient needs. Registration will be done using a pre-prepared form.
6. Follow-up examination. Done by calibrated examiner (postdoctoral researcher).

Deliverables of WP4

D4.1 Enrolment registration form.

D4.2 Signed informed consent forms.

D4.3 Initial patient examination forms (including parent questionnaire).

D4.4 Intervention registration forms (including Visual Analogue Scale [VAS] of patient satisfaction).

D4.5 Emergency treatment forms (including VAS of patient satisfaction).

D4.6 Follow-up examination forms (including VAS of patient acceptance and Likert scale questions of parents acceptance).

Milestones of WP4

MS4.1 Meetings about enrollment, randomization and allocation.

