D6.2 Conference abstracts.

D6.3 Publication about the effectiveness of SDF and Tiefenfluorid treatment in preschool children with S-ECC (to be published in Caries Research (impact factor: 2.188) or in BMC Oral Health (impact factor: 1.602).

D6.4 Publication about the effectiveness of fluoride treatment according to the type of carious lesion in deciduous dentition (to be published in the International Journal of Paediatric Dentistry (impact factor: 2.18) or in European archives of paediatric dentistry: official journal of the European Academy of Paediatric Dentistry (impact factor: 1.48).

D6.5 Evidence-based recommendations and economic evaluation report for national policymakers.

Milestones of WP6

MS6.1 Meeting with Communication Department and IT department of RSU.

MS6.2 Scientific conferences.

MS6.3 Meeting with policymakers.

Gantt chart

The workflow in each work packages and relevant deliveries are illustrated in the Gantt chart (Fig 4.).

[figure not shown]

Fig 4. The Gantt chart of the clinical trial.

Risks

1. Research achievability risks
 - a. Number of patients recruited less than expected - sample size calculation was estimated using conservative assumptions. The expected difference in the prevalence of severe caries complications in different treatment groups and the placebo group is expected to be 20% (10% complication rate for treatment groups and 30% for placebo). From previous studies, the expected prevalence in treatment groups could be even less, meaning the observed difference would be greater. In such a case, statistical power can be achieved even with a lower number of patients.
 - b. Loss of follow-up – we plan to include 70 patients in every group in order to ensure that there are still at least 49 in every group at the end of the project (we assume the potential loss of follow-up examinations to be 30%, which we consider to be sufficient).
2. Research methodology risks

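### Deleting missing data is the only stated rule although 30% loss is expected, and nothing lets emergency-form complications stand in for a missed 12-month visit

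*Protocol*

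**What the plan says.** - **Missing data** (Protocol, Statistical analysis): "Missing data will be eliminated from the analyses, marking them NA". No other handling is given anywhere in the document.
- **Expected loss** (Protocol, Risks, 1b): "we plan to include 70 patients in every group in order to ensure that there are still at least 49 in every group", with the explanation "we assume the potential loss of follow-up examinations to be 30%, which we consider to be sufficient". Risks 2a adds a further source of loss. Children treated by a dentist not trained for the study are left out of the analysis when the record of that treatment is in doubt, and over-enrolment is again the answer.
- **Primary outcomes** (Protocol, Outcome variables, I.A to I.C): pain (yes/no), abscess (yes/no) and the number of teeth extracted or otherwise surgically treated. All three cover the observation period and are assessed at the 12-month visit.
- **Emergency records** (Protocol, Work packages): WP4 task 5 is "Performing and documenting emergency treatment during the follow-up period", carried out by general staff. The form is deliverable D2.3 and the completed forms are D4.5. The Ethics section and WP5 say that forms will be digitised. No section says that these records supply a primary outcome when the 12-month visit is missed.
- **Lesion outcome** (Protocol, Outcome variables, II.B): "The progression and change of activity of every lesion", scored by ICDAS and Nyvad at 12 months. The text gives no rule for a tooth that is no longer there.

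**The concern.** Over-enrolment protects power, not validity. After deletion, each group's complication proportion is that of the children who came back. It equals the proportion among all randomised children only if, within that group, loss is unrelated to having a complication.

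Such a relation is plausible here. A child who needed urgent care elsewhere may well be one with a complication, and Risks 2a can remove that child. The waiting list for treatment under general anaesthesia lasts 12 months (Participants), the same length as follow-up, so some children may have had definitive treatment by the time they are due back.

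The trial also collects, as events happen, part of the information that the missed visit would have given. The plan provides no route from those forms to the primary outcomes. A child with an abscess or extraction on record at the institute could therefore be marked missing on that very outcome and dropped.

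At stake are all three primary outcomes. The expected missing share in each group (30%) is larger than the 20-point difference that the trial is sized to detect.

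**Working it through.** **Inputs from the Protocol.** 70 enrolled and 49 retained per group and 30% loss (Risks, 1b); 30% complications on placebo and 10% on treatment (Sample size calculation). As in that section, a complication is treated as yes/no.

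**1. The plan's own figure.** 49 / (1 - 0.30) = 70 per group and 6 x 70 = 420, as stated. Loss is 70 - 49 = 21 per group, or 6 x 21 = 126 children. Whether 49 is itself the right number is a separate question and is not used here.

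**2. Complications removed if loss is unrelated to outcome.** A placebo group of 70 has 0.30 x 70 = 21 children with complications, of whom 0.30 x 21 = 6.3 are deleted. A treated group has 0.10 x 70 = 7, of whom 0.30 x 7 = 2.1 are deleted. The proportions stay at 30% and 10%, so there is no bias in this case.

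**3. Extreme limits.** Suppose the 49 completers show 30% and 10%, that is 14.7 and 4.9 events.

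- Placebo, all 70: from 14.7/70 = 21% (no lost child has an event) to (14.7 + 21)/70 = 51% (every lost child has one).
- Treated, all 70: from 4.9/70 = 7% to (4.9 + 21)/70 = 37%.
- Difference: from 21 - 37 = -16 points to 51 - 7 = +44 points.

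The width is 60 points, which is 42 lost children / 70. Each lost child whose outcome becomes known narrows it by 1/70, or 1.4 points.

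**4. Moderate scenarios (assumed).** Let children with complications be k times as likely to be lost as the others, with 30% loss in every group. The value of k is not in the documents. With true proportion p, loss among children without complications is d = 0.30 / (pk + 1 - p), and the proportion seen in completers is p(1 - kd) / 0.70. For k = 2:

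- Placebo: d = 0.30/1.30 = 0.231, kd = 0.462, seen 0.30 x 0.538/0.70 = 23.1%.
- Treated: d = 0.30/1.10 = 0.273, kd = 0.545, seen 0.10 x 0.455/0.70 = 6.5%.

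| k (assumed) | Placebo seen | Treated seen | Difference seen (true: 20 points) |
|---|---|---|---|
| 0.5 | 35.3% | 12.0% | 23.3 |
| 1 | 30.0% | 10.0% | 20.0 |
| 1.5 | 26.1% | 8.2% | 17.9 |
| 2 | 23.1% | 6.5% | 16.6 |
| 3 | 18.8% | 3.6% | 15.2 |

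At k = 2 about 9.7 of the 21 placebo complications and 3.8 of the 7 treated ones are deleted. If k = 2 held in the placebo group only, the difference seen would be 23.1 - 10.0 = 13.1 points. If it held in the treated group only, it would be 30.0 - 6.5 = 23.5 points. The error can go either way.

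**The case against.** **A reader might infer that the plan throws away complications on the emergency forms. The documents do not say so.** The rule removes missing data, and a documented abscess is arguably not missing. The forms are deliverables and are to be digitised. This objection stands: the use of the forms is unspecified, and their discarding is not stated. But with outcome assessment tied to the 12-month visit and deletion as the only rule, an analyst following the text has no instruction to use them.

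**It is equally tempting to say that the outcome is already known for many lost children.** No count supports that. With loss unrelated to outcome, about 6 of the 21 children lost from a placebo group and 2 of the 21 lost from a treated group would have any complication. Fewer would have a form, because it records only emergency treatment.

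**Nor can one say that the worst lesions are dropped from II.B.** WP2 (task 6, D2.6) plans an adaptation of ICDAS and Nyvad, and the examination forms are not shown, so a code for extracted teeth may exist. In children who attend, extractions count in primary outcome C anyway. This part touches secondary outcomes only.

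**Staining does not by itself show bias.** The information for parents says that the treatments can darken teeth, SDF especially, and Risks 2c notes that arrested lesions darken without any agent. Loss that depends on group alone leaves each group's proportion unbiased; a link to complications within the group is needed.

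**The limits of -16 and +44 are extreme.** They require every lost child in one group and none in the other to have an event, and imputation does not remove them. That is correct. They show what the data alone cannot exclude, not what is likely.

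**An imputation model is ordinary SAP content.** True, and its absence is no fault. The fault is that the Protocol fixes a rule, and the rule is deletion.

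**Conclusion.** The point holds in this form. Deletion is the only stated rule for missing data, 21 of 70 children per group are expected to be lost, and over-enrolment is the only response. Followed as written, the plan gives a complete-case primary analysis that is exposed to any relation between loss and complications within a group, and it makes no provision for complications already documented.

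The direction and size of the bias are not determined by the documents. With completers at 30% and 10%, the extreme limits are -16 and +44 points. Under the assumed values of k from 0.5 to 3, applied to all groups, a true 20-point difference would appear as 23.3 down to 15.2 points, and as 16.6 at k = 2. These scenarios assume equal 30% loss in each group and the planned complication rates. They do not show that a benefit would be falsely claimed.

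**What to change.** Replace the deletion sentence in Statistical analysis with these rules, before any results by group are seen:

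1. A complication documented on an emergency form counts as an event even without the 12-month visit, identically in all six groups. The absence of a form is not a No; those children remain missing and go to step 2. Events noted only at intervention visits are not used. Only the two-application groups have a 6-month visit, the four-application groups have none between week 3 and month 12, and the intervention staff know the product.
2. All randomised children are analysed in their allocated group. Remaining missing primary outcomes are multiply imputed by group from baseline caries, age and recorded events, with best- and worst-case sensitivity analyses by arm. The exclusion in Risks 2a must be brought into line.
3. Complete-case analysis is a sensitivity analysis only.
4. For II.B, unless the adapted ICDAS/Nyvad forms already code it, lesions on teeth extracted for caries count as progressed, not as NA. II.F separates extraction (major, patient level) from lesion progression (minor, tooth level), so it should state that an extraction counts once, as a major complication.

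The cost is wording and slightly more analysis work; the emergency forms are already planned. The downside is reliance on the imputation model, which the sensitivity analyses in steps 2 and 3 make visible but do not remove.

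### Risk 1a says lower complication rates in the active groups would preserve power with fewer children; by the plan's own formula this fails against placebo at the planned size, and it gives no cover for the agent and schedule comparisons

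*Protocol*

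**What the plan says.** Protocol, Risks, item 1a deals with recruiting fewer patients than expected. It calls the sample-size assumptions conservative and restates them as "10% complication rate for treatment groups and 30% for placebo". It adds that the active rate could be lower still, which would widen the difference, and ends: "In such a case, statistical power can be achieved even with a lower number of patients".

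Protocol, Sample size calculation, sets the inputs behind that statement: "with α error 0.05 and with a study capacity of 80" per cent, and a Bonferroni-type formula (Fig 1), "calculating that the planned number of various proportions for comparison will be 9". It arrives at 49 evaluable children per group, with 70 enrolled to allow for losses.

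Two other places define what the trial is meant to compare. The sample-size question is "Which of the applied caries treatment methods will have the least frequency of complication occurrences". The primary aim, under Work packages, WP4, is to find "which high-concentration fluoride application method and which application protocol more effectively protects pre-school children from complications". Study design and settings also names a comparison with placebo.

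**The concern.** Risk 1a makes a positive statement about power, and two things about it need checking.

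First, it names no threshold. Any active rate under 10% appears to be enough, although the number that Fig 1 requires may still exceed 49 over much of that range.

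Second, it reasons only from the gap between active and placebo. The primary aim asks which agent and which schedule does better, and those are comparisons among active groups. All active groups share one planning rate of 10%, so the plan assumes no difference between them. A fall in the active rates widens the gap to placebo but need not widen any gap between active groups.

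At stake is whether the sponsor can rely on this sentence if recruitment falls short. If it is wrong, the trial could be described as adequately powered when it is not.

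**Working it through.** **Inputs.** Two-sided α = 0.05, τ = 9 comparisons, 80% power, placebo 30%, active 10%, 49 evaluable per group (Protocol, Sample size calculation and Fig 1). The other active rates below are assumptions; the protocol gives none.

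**Formulas (Fig 1).**

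- n = [pA(1−pA) + pB(1−pB)] × [(z₁₋α/(2τ) + z₁₋β)/(pA−pB)]²
- Power = Φ(z − z₁₋α/(2τ)) + Φ(−z − z₁₋α/(2τ)), with z = |pA−pB| / √{[pA(1−pA) + pB(1−pB)]/n}

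The critical value is z at 1 − 0.05/18 = 2.773, and z at 0.80 is 0.842. The squared sum is 13.065.

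**Step 1: the plan's own figure.** For 30% versus 10%: (0.21 + 0.09) × 13.065 / 0.04 = 97.99, so 98. The stated 49 is half of this. The Fig 1 legend describes n as covering two groups, which would explain the halving. But Fig 1's power formula divides each group's variance by n, so n is per group. At n = 49, z = 0.20/√(0.30/49) = 2.556 and power is 41%. At n = 98 it is 80%.

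**Step 2: active versus placebo (30%) at lower active rates.**

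| Active rate | n per group for 80% power | Power at 49 | at 45 | at 40 | at 35 |
|---|---|---|---|---|---|
| 10% | 98 | 41% | 37% | 32% | 27% |
| 8% | 77 | 55% | 50% | 44% | 37% |
| 5% | 54 | 75% | 70% | 63% | 56% |

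The required number falls as the active rate falls, so the direction in Risk 1a is right. Setting n = 49 and solving for the active rate gives 4.18%. Between that value and 10%, 49 per group is already too few, and a smaller number is worse.

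**Step 3: active versus active, same formula, τ = 9.**

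| Scenario (assumed rates) | n per group | Power at 49 |
|---|---|---|
| Halving, 10% vs 5% | 719 | 3.4% |
| Halving, 5% vs 2.5% | 1,503 | 1.7% |
| Same 5-point gap, 6% vs 1% | 347 | 7.9% |
| One agent improves, 10% vs 2% | 224 | 14.0% |

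At a constant ratio, halving the rates roughly doubles the number needed. At a fixed absolute gap, or if only one agent improves, the number falls relative to 10% versus 5%. Every entry far exceeds 49. Without multiplicity adjustment the four figures are 432, 903, 209 and 135, which is the same pattern and also above 49.

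**The case against.** There are four fair points on the other side.

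1. Risk 1a names active versus placebo, the contrast that the sample size uses, and for that contrast its direction is correct. This stands. A reader might infer that the contingency works backwards; for the comparison it describes, it does not.

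2. Lower active rates do not always make agent and schedule comparisons harder. That holds at a constant relative effect and reverses at a fixed absolute gap or if only one agent improves. This also stands, and the protocol gives no active-versus-active rates that would settle which case applies. The conclusion has to be that lower rates do not protect these comparisons, not that they must harm them.

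3. The 4.2% threshold arises because 49 is half of what Fig 1 gives. On the plan's halved reading, any active rate under 10% would need fewer than 49 (8% gives 76.6/2 = 38.3). With no multiplicity adjustment, 5% would need only 33. This is true, and it means Risk 1a cannot be corrected separately from the sample-size statement. It does not rescue the sentence: Fig 1's power formula does not support the halving, and the plan states 9 comparisons.

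4. The text says that power can be achieved in such a case. A reader might infer that it treats a shortfall as harmless or allows recruitment to close early. It says neither, and the target of 70 per group is unchanged. Nor does the protocol say that a null result between agents would be read as equality.

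One might also pool the two schedules to compare agents, giving 98 per agent. At unadjusted α = 0.05, power is then 27% for 10% versus 5% and 15% for 5% versus 2.5%, so pooling does not change the conclusion for these halving scenarios.

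**Conclusion.** The point holds in a limited form. Risk 1a states a power property that the plan's own formula contradicts over most of the range it invokes: at 49 evaluable per group, power against placebo is 41% to 75% for active rates from 10% down to 5%, and reaches 80% only at about 4.2%. This rests on Fig 1 as printed, τ = 9 and a 30% placebo rate, and is tied to the finding that 49 is half the 98 that Fig 1 requires. For the same reason, calling the assumptions conservative does not support the reassurance.

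Separately, the argument does not reach the agent and schedule comparisons in the primary aim. The size of that gap depends on assumed rates, but in each scenario shown the pairwise requirement (224 to 1,503 per group) is several times 49. Those comparisons are short of power in these scenarios even with full recruitment, so the fault in Risk 1a is that it offers cover it cannot give, not that it causes the shortage. The correction is worth making and is confined to a few sentences.

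**What to change.** In Risks, item 1a:

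- Delete the description of the assumptions as conservative and the sentence saying that power can be kept with fewer patients.
- State that a shortfall lowers power, and give the Fig 1 power at 49, 45, 40 and 35 evaluable children per group for active rates of 10%, 8% and 5% against 30% (the Step 2 values). Make this agree with a corrected sample-size statement, so that the table does not stand beside an uncorrected 49.
- State that active rates below 10% help only the placebo comparisons and do not protect the comparisons of agents and schedules.

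A rule for reporting null results between active groups is optional and could be left to the analysis plan.

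Cost: protocol wording and one small table. The stated reassurance becomes less favourable. This change itself needs no extra patients; whether to enlarge the trial belongs to the sample-size correction.

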 - a. Patients received treatment outside the RSU Institute of Stomatology – every case will be analysed separately; if, for any reason, the patient attended a dentist who was not trained for the study (in the Institute of Stomatology or in another dental clinic), the recordings of treatment performed will be analysed – if there is no doubt regarding the information gained and if the treatment was done according to the guidelines used in the study, the patient will be kept in the study. In case of doubt, he/she will be excluded from analysis. This increases the risk of loss of follow-up, but it is important that we are sure about the impact of the treatment performed. Evenmore, as described above, we will include more patients than required to assure the study power even after some losses of follow-up.
 - b. Blinded research team members are informed about colour codes of the treatment groups – we will consider changing the person in case the this knowledge leads to performance or detection bias. We also will include as less personal as possible and the most motivated colleagues to avoid such errors.
 - c. Patients find out which treatment group they have been assigned to– it is possible that the groups which receive SDF “feel” the treatment to be more effective because of the staining side effect. However, we are not yet sure how important this effect will be, as all of those children have tooth damage which includes some colour change of the lesions. It is also known that arrested lesions tend to become darker even without the application of any agent. We will be able to address this risk by evaluating the patient and parent satisfaction in different treatment groups.

Infrastructure

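### Excluding doubtful cases of outside dental treatment after randomisation can selectively remove children with primary-outcome events; the size and direction of the resulting bias are unknown

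*Protocol*

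**What the plan says.** Risks, item 2a, applies to visits to an untrained dentist inside or outside the Institute: "every case will be analysed separately; if, for any reason, the patient attended a dentist who was not trained for the study", the records of that treatment are examined. The child stays "if there is no doubt regarding the information gained and if the treatment was done according to the guidelines used in the study". Otherwise: "In case of doubt, he/she will be excluded from analysis". The text does not say what counts as doubt, who decides, or whether that person is blind to group. It sees the consequence as a loss of numbers only and answers that "we will include more patients than required to assure the study power even after some losses of follow-up".

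The primary outcomes (Outcome variables, part I) are:

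- "Pain history during the observation period, assessed as Yes/No at 12 months follow-up visit"
- "Abscess history during the observation period, assessed as Yes/No at 12 months follow-up visit"
- "The number of newly extracted or otherwise surgically treated teeth during the observation period", recorded as a count at the same visit.

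The Statistical analysis section drops missing data. The protocol nowhere says that all randomised children are analysed in their allocated group.

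**The concern.** A child on a waiting list who visits another dentist may well do so because of pain, abscess or a tooth that needs extraction. The third primary outcome is itself dental treatment, so one extraction elsewhere can be both a primary event and the trigger for possible exclusion. The judgement is made from treatment records, that is, after the event is known.

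The exclusion could also differ by group. Intervention staff know which product each group receives (Randomization, allocation and blinding). Risks item 2c accepts that staining may reveal SDF allocation, and families' beliefs about treatment may affect where they seek care. With the decision not stated to be blinded, nothing in the text prevents knowledge of the group from entering it.

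Exclusion also discards usable data. Pain and abscess are histories taken at 12 months and extractions are a 12-month count, so a child with unclear outside records who attends follow-up can often still supply an outcome.

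**Working it through.** **Inputs from the protocol.** Complication rates of 30% (placebo) and 10% (active), 49 children needed and 70 enrolled per group (Sample size calculation); 30% loss to follow-up (Risks, item 1b).

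**Inputs assumed.** q is the share of children with an event who are excluded. The documents give no figure, so 6% to 50% is shown. The low end corresponds, for example, to 20% of event children seeing an untrained dentist and 30% of those cases being in doubt: 0.20 × 0.30 = 0.06. No event-free child is assumed to be excluded. The 30% and 10% refer to complications overall, so the illustration fits a yes/no outcome and not the tooth count.

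**Step 1, the plan's reserve.** 70 × (1 − 0.30) = 49, as stated. This reserve replaces numbers; it does not restore the mix of children with and without events.

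**Step 2, equal exclusion in both arms.** Observed rate = p(1 − q)/(1 − pq). For q = 0.30: placebo 0.30 × 0.70/(1 − 0.09) = 0.231; active 0.10 × 0.70/(1 − 0.03) = 0.072.

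| q in both arms | Placebo | Active | Difference (points) |
|---|---|---|---|
| 0 | 30.0% | 10.0% | 20.0 |
| 6% | 28.7% | 9.5% | 19.3 |
| 10% | 27.8% | 9.1% | 18.7 |
| 30% | 23.1% | 7.2% | 15.9 |
| 50% | 17.6% | 5.3% | 12.4 |

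Differences are taken before rounding. The observed odds are p(1 − q)/(1 − p), so an equal q cancels in the odds ratio, which stays at (0.30/0.70)/(0.10/0.90) = 3.86. If the true rates are equal, the observed rates are equal too.

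**Step 3, unequal exclusion.**

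| True rates | q placebo | q active | Observed | Difference (points) |
|---|---|---|---|---|
| 30% v 10% | 50% | 10% | 17.6% v 9.1% | 8.6 |
| 30% v 10% | 30% | 0 | 23.1% v 10.0% | 13.1 |
| 30% v 10% | 0 | 30% | 30.0% v 7.2% | 22.8 |
| 30% v 30% | 0 | 30% | 30.0% v 23.1% | 6.9 (false) |
| 30% v 30% | 0 | 50% | 30.0% v 17.6% | 12.4 (false) |

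In the two rows without a true effect, with 49 per arm before exclusion, the protocol's power formula gives rejection rates of about 12% and 29% at an unadjusted two-sided 0.05. With the planned division by nine comparisons they are 2.2% and 8.5%, against a nominal 0.05/9 = 0.56%.

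**Step 4, if event-free children are excluded too.** With q₁ for event and q₀ for event-free children, the observed rate is p(1 − q₁)/[p(1 − q₁) + (1 − p)(1 − q₀)]. If q₁ = q₀ within each arm, this is p and there is no bias. The bias therefore depends on doubt falling more often on children with events.

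**The case against.** The written trigger is not the outcome. It is a visit to an untrained dentist for any reason, followed by doubt about the information or about adherence to the guidelines. A child whose outside extraction is clearly documented and conforms to the guidelines stays in, and an outside visit for something other than a primary event would also come under review. A reader might infer that children are removed because they had the primary outcome; the text does not say that. It supports only that the rule can remove such children.

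The main route for complications is also untouched. Emergencies are treated at the Institute (Ethics), by general staff trained for the purpose (WP3) and on a prepared form (WP4). The rule reaches a remainder: children seen by an untrained dentist and left in doubt. That remainder may be small. At q = 6% the difference falls by only 0.7 points.

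These points stand, and they limit what can be claimed about size. They do not remove the defect: the exclusion is fixed in current text, its criteria are undefined, its blinding is unstated, and nothing elsewhere brings the excluded children back. A separate statistical analysis plan might define an all-randomised set, but it would then conflict with this passage. Dependence on group is possible, not shown; the 12-month examiner is described as unaware of the treatment, but the protocol does not assign the decision on doubtful cases to that person.

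**Conclusion.** The concern holds in a limited form. Followed as written, the rule can bias the primary comparison by selectively removing children with events, and over-enrolment is no protection. Neither size nor direction can be read from the protocol. On the planning rates, with no event-free child excluded, equal removal of 6% to 50% of event children costs between 0.7 and 7.6 points of a 20-point difference. It pulls the risk difference towards zero, leaves the odds ratio alone and creates no false effect. Unequal removal can shrink, enlarge or create a difference.

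A reader might conclude that the randomised comparison is lost, or that a benefit will vanish or be manufactured. The documents do not support that. The larger distortions come from assumed, markedly unequal exclusion shares, and the affected subset may be small. The change is still needed before analysis, because the rule bears directly on the primary outcomes and replacing it is cheap.

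**What to change.** Rewrite Risks, item 2a, and carry the change into the Statistical analysis section:

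- Remove the exclusion from the primary analysis. Analyse every randomised child with 12-month outcome data in the allocated group, whichever dentist was seen.
- Count pain, abscess and extracted or surgically treated teeth from any clinic towards the respective primary outcome.
- Set criteria for doubtful records in advance, and have existing staff who are blind to group classify them.
- Add a sensitivity analysis: doubtful pain and abscess cases set to yes and then to no; doubtful extractions counted and then not counted, since that outcome is a number of teeth.
- Keep the present exclusion only as a secondary per-protocol analysis.

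The cost is wording and some time of existing staff for the blinded classification. The protocol already has outside records examined, so no new visits are needed. The change does not solve the separate problem of children lost to follow-up, who have no 12-month outcome.
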